4.2 METHOD OF TREATMENT ASSIGNMENT AND BLINDING

Patients will be randomly assigned to one of three active, IV dose arms (1500, 4500, or 8100 mg MTAU9937A) or to an IV placebo dose arm in a 2:3:2:3 (1500mg:4500 mg: 8100 mg:placebo) ratio. Randomization of patients will be managed by a central interactive voice or Web-based response system (IxRS) vendor using stratified permuted block randomization. The randomization will be stratified by dementia status (pAD vs. mAD) and APOE status (ApoE4+ vs. ApoE4-).

Patients, study site personnel who will evaluate patient status, contract research organization (CRO) personnel who will review CRFs, other Sponsor agents (with the exception of the IxRS vendor), and the Sponsor will remain blinded to treatment assignment. The unblinded site pharmacist and the unblinded CRO monitor will be unblinded to treatment assignment.

The iDMC and independent data coordinating center vendor will be unblinded to treatment assignment.

Although PK samples must be collected from participants assigned to placebo to maintain the blinding of treatment assignment, PK assay results for the placebo participants are generally not needed for the safe conduct or proper interpretation of this trial. Laboratory personnel responsible for performing PK assays will be unblinded to participants' treatment assignments to identify appropriate PK samples to be analyzed. Samples from participants assigned to the placebo arm will not be analyzed except by request (e.g., to evaluate a possible error in dosing).

If unblinding is necessary for immediate patient management (e.g., in the case of a serious adverse event for which patient management might be affected by knowledge of treatment assignment), the investigator will be able to break the treatment code by contacting the IxRS. The investigator is not required to contact the Medical Monitor prior to breaking the treatment code; however, the treatment code should not be broken except in emergency situations. If the investigator wishes to know the identity of the study drug for any reason other than a medical emergency, he or she should contact the Medical Monitor directly. The investigator should document and provide an explanation for any non-emergency unblinding. The investigator will be able to break the treatment code by contacting the IxRS.

As per health authority reporting requirements, the Sponsor's Drug Safety representative will break the treatment code for all serious, unexpected suspected adverse reactions (see Section 5.7) that are considered by the investigator or Sponsor to be related to study drug. The patient may continue to receive treatment, and the investigator, patient, and Sponsor personnel, with the exception of the Drug Safety representative and personnel who must have access to patient treatment assignments to fulfill their roles (as defined above), will remain blinded to treatment assignment.

4.3 STUDY TREATMENTS RELEVANT TO THE STUDY DESIGN

MTAU9937A is an investigational medicinal product (IMP) in this study. Depending on local classification, the [¹⁸F]GTP1 tau PET radioligand and/or the amyloid PET radioligand(s) may be considered non-investigational medicinal products (NIMPs) or IMPs. Refer to the Amyloid Imaging Technical Operations Manual for a list of amyloid PET radioligands allowed in this study.

4.3.1 Study Treatment Formulation, Packaging, and Handling

4.3.1.1 MTAU9937A and Placebo

MTAU9937A will be supplied by the Sponsor as a sterile liquid in 20-mL glass vials. For information on the formulation and handling of MTAU9937A, see the pharmacy manual and the MTAU9937A Investigator's Brochure.

4.3.1.2 [¹⁸F]GTP1 Tau PET Radioligand

[¹⁸F]GTP1 will be provided under contract with a PET imaging vendor in accordance with approved national and/or local standards. [¹⁸F]GTP1 will be supplied as a sterile non-pyrogenic solution in sterile borosilicate glass vials with gray butyl septa and aluminum ring seals. The vial is contained within an outer lead or tungsten shield ("pig") to protect from gamma radiation. The final product bears a label with the following items: total activity (mCi), volume (mL), strength (mCi/mL), calibration date and time, batch number, study identification, and shelf life. For information on the formulation and handling of [¹⁸F]GTP1, see the [¹⁸F]GTP1 Investigator's Brochure and the [¹⁸F]GTP1 PET Imaging Technical Operations Manual.

4.3.1.3 Amyloid PET Radioligands

Appropriate amyloid PET radioligands will be provided under contract with a PET imaging vendor and/or PET radioligand producers in accordance with approved national and/or local standards. Refer to the local labeling instructions or, depending on locality, the Investigator's Brochures, for details on packaging, formulation, and handling of the amyloid PET radioligands. Depending on locality, additional information may also be found in the local labeling information or the Investigator's Brochure for the particular amyloid PET radioligand being used.

4.3.2 Study Treatment Dosage, Administration, and Compliance

The treatment regimens are summarized in Section [3.1.1](#).

Any overdose or incorrect administration of MTAU9937A or [¹⁸F]GTP1 or an amyloid radioligand (if they are considered IMPs) should be noted on the Study Drug Administration eCRF. Adverse events associated with an overdose or incorrect administration of any of the study treatments should be recorded on the Adverse Event eCRF.

Guidelines for dosage modification and treatment interruption or discontinuation for patients who experience adverse events are provided in Section [5.1.3](#).

4.3.2.1 MTAU9937A and Placebo

MTAU9937A will be prepared and diluted into 100-mL IV bags according to the pharmacy manual, and infusions will be administered per the instructions outlined in [Table 2](#) and the pharmacy manual.

Table 2 Administration of First and Subsequent Infusions of MTAU9937A

First Infusion	Subsequent Infusions

 • Begin infusion at an initial rate of 0.5 mL/min (30 mL/hr). • If no infusion-related or hypersensitivity reaction occurs during the first 30 minutes, then increase the rate to 1.0 mL/min (60 mL/hr). • If no infusion-related or hypersensitivity reaction occurs during the subsequent 30 minutes, then increase the rate to 3.0 mL/min (180 mL/hr) • If a reaction develops, stop or slow the infusion. Administer medications and supportive care in accordance with institutional guidelines. The patient should be monitored until all infusion-related adverse events are Grade 1 or are resolved. 
If the reaction resolves, resume the infusion at a 50% reduction in rate (i.e., 50% of rate being used at the time that the reaction occurred). If the reaction recurs after resumption of the infusion, then stop the infusion. For patients who experience serious or severe hypersensitivity or hypersensitivity-like reactions (e.g., hypotension, mucosal involvement), the investigator must discuss with the Medical Monitor whether to continue study drug treatment.
	
 • If the participant experienced an infusion-related or hypersensitivity reaction during the prior infusion, begin infusion at an initial rate of 0.5 mL/min and follow instructions for first infusion. • If the participant tolerated the prior infusion well (defined by an absence of Grade 2 reactions during a final infusion rate of 3.0 mL/min), begin infusion at a rate of 3.0 mL/min. • If a reaction develops, stop or slow the infusion. Administer medications and supportive care in accordance with institutional guidelines. The patient should be monitored until all infusion-related adverse events are Grade 1 or are resolved. 
If the reaction resolves, resume the infusion at a 50% reduction in rate (i.e., 50% of rate being used at the time that the reaction occurred). If the reaction recurs after resumption of the infusion, then stop the infusion. For patients who experience serious or severe hypersensitivity or hypersensitivity-like reactions (e.g., hypotension, mucosal involvement), the investigator must discuss with the Medical Monitor whether to continue study drug treatment.

4.3.2.2 [18F]GTP1 Tau PET Radioligand

Patients who undergo tau PET imaging will receive [18F]GTP1 and undergo a PET scan on multiple occasions as described in the schedule of activities in [Appendix 1](#) and [Appendix 2](#). Refer to the [18F]GTP1 PET Imaging Technical Operations Manual for details on the use of [18F]GTP1.

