5.1.1 Potential Risks Associated with MTAU9937A

5.1.1.1 Infusion-Related Reactions or Hypersensitivity

Monoclonal antibodies such as MTAU9937A may be associated with a potential immune response in clinical trials, such as hypersensitivity or hypersensitivity-like reactions, including severe, anaphylactic reactions (see Appendix 5 for precautions). Study sites will be prepared to manage any hypersensitivity or hypersensitivity-like events.

All participants will be monitored for infusion reactions, hypersensitivity, or hypersensitivity-like reactions during the infusion and immediately afterwards (see Section 5.1.3.2 for additional instructions on monitoring and management of infusion reactions).

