5.1.3.2 Management Guidelines for Infusion-Related Reactions

In the event that a participant experiences a mild infusion-related reaction, the infusion may be halted. Once the reaction has resolved, the infusion rate will be resumed at half of the most recently used rate (e.g., from 60 mL/hr [1.0 mL/min] to 30 mL/hr [0.5 mL/min]; see Section 4.3.2.1). Patients who experience a moderate-to-severe infusion-related reaction (e.g., fever or chills) should have their infusion stopped immediately and should receive aggressive symptomatic treatment. The patient should be monitored until all

infusion-related adverse events are Grade 1 or are resolved. The infusion should not be restarted before all symptoms have disappeared, and then it should be restarted at half the initial rate. The infusion should not be resumed if there is a second occurrence at the same visit or if the patient experiences any of the following: mucosal tissue involvement, airway compromise, or symptomatic hypotension with systolic blood pressure <90 measured in the supine position. In the case of any serious or severe infusion-related reaction, the investigator must discuss with the Medical Monitor whether to continue study drug treatment (see Section 4.3.2.1 for further details).

For patients who experience a serious or severe hypersensitivity or hypersensitivity-like reaction (e.g., hypotension, mucosal involvement), the investigator must discuss with the Medical Monitor whether to continue study drug treatment (see Section 4.3.2.1 for further details).

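### Table 2 tells staff to restart the infusion once a reaction resolves and omits the three clinical bars to restarting set in Section 5.1.3.2

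*Protocol*

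**What the plan says.** Section 4.3.2.1 states that "infusions will be administered per the instructions outlined in" Table 2 and the pharmacy manual. Table 2 has one column for the first infusion and one for later infusions, and both handle a reaction in the same way. The opening step is "If a reaction develops, stop or slow the infusion", with no limit by grade or type. The next is "If the reaction resolves, resume the infusion at a 50% reduction in rate", meaning half the rate in use when the reaction occurred. If the reaction comes back after that, the infusion is stopped. For serious or severe hypersensitivity-type reactions, with hypotension and mucosal involvement as examples, the investigator must also talk to the Medical Monitor about whether study drug should continue.

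Section 5.1.3.2 covers the same events. On stopping, it says: "Patients who experience a moderate-to-severe infusion-related reaction (e.g., fever or chills) should have their infusion stopped immediately". On resuming, it says: "The infusion should not be resumed if there is a second occurrence at the same visit or if the patient experiences any of the following", and the list that follows is "mucosal tissue involvement, airway compromise, or symptomatic hypotension with systolic blood pressure <90 measured in the supine position". It also requires the Medical Monitor discussion for serious or severe reactions.

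Two other places link the sections. Section 4.3.2 says: "Guidelines for dosage modification and treatment interruption or discontinuation for patients who experience adverse events are provided in Section" 5.1.3. Section 5.1.1.1 refers to Section 5.1.3.2 "for additional instructions on monitoring and management of infusion reactions".

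**The concern.** Take a patient whose airway symptoms during an infusion have resolved. Table 2 tells the person at the bedside to restart at half rate. Section 5.1.3.2 says not to restart. Both cannot be followed, and the table used for giving the infusion carries the less cautious instruction.

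What is at stake is re-exposure to an antibody infusion, at the same visit, after the features the sponsor itself singled out as reasons not to continue. Section 5.1.1.1 names severe, anaphylactic reactions as a potential risk, and Section 5.2.3 makes infusion reactions of Grade 3 or higher an adverse event of special interest. Enrollment is complete, but dosing is not confined to the past. Each patient has up to 19 double-blind doses, and those who continue then receive open-label drug every 4 weeks for up to 96 weeks. The conflict sits in the column for later infusions as well as the first.

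**Working it through.** No arithmetic beyond a count applies, so the two texts are set side by side.

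| Situation | Table 2 (both columns) | Section 5.1.3.2 | Agree? |
|---|---|---|---|
| Second occurrence at the visit | Stop | Do not resume | Yes |
| Mucosal involvement, resolved | Resume at half rate; consult Medical Monitor if serious or severe | Do not resume | No |
| Airway compromise, resolved | Resume at half rate; not named | Do not resume | No |
| Symptomatic hypotension, supine systolic below 90, resolved | Resume at half rate; consult Medical Monitor if serious or severe | Do not resume | No |
| Moderate-to-severe reaction at onset | Stop or slow | Stop at once | Only if staff choose to stop |

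**Count of bars to resumption.** Section 5.1.3.2 lists 1 + 3 = 4. Table 2 carries 1 (recurrence), so 4 − 1 = 3 are missing. Of those 3, Table 2 names 2 as triggers for a discussion and leaves 1 (airway compromise) unnamed.

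**Does the Medical Monitor step stand in for the missing bars?** No. In Table 2 that step concerns whether study drug continues. Section 5.1.3.2 requires the same discussion and still states the bar, so the protocol treats them as separate decisions. Even if the step is read as covering restart at the same visit, Table 2 would allow a restart after discussion where Section 5.1.3.2 allows none.

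**Do the cross-references settle it?** No. Sections 4.3.2 and 5.1.1.1 point towards Section 5.1.3 and 5.1.3.2 but set no order of precedence. Section 5.1.3.2 refers back to Section 4.3.2.1, which holds the table without the bars. Appendix 5 says to stop for suspected anaphylaxis and does not address resumption.

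**Stop or slow.** This is a permissive conflict. Stopping satisfies both texts, whereas slowing a moderate-to-severe reaction satisfies only Table 2.

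**A related difference in the same two places.** After a moderate-to-severe reaction, Section 5.1.3.2 restarts at half the initial rate, for example 0.5 / 2 = 0.25 mL/min. Table 2 restarts at half the rate in use, for example 3.0 / 2 = 1.5 mL/min. This does not bear on the bars, but one edit should cover both.

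**The case against.** The best counter-argument is that the sections are meant to be read together, with Table 2 as the default and Section 5.1.3.2 supplying the exceptions. The parent section of Table 2 sends the reader to Section 5.1.3, and an investigator who consulted both would probably apply the stricter rule. That lowers the practical risk. It does not remove the conflict, because Table 2 gives an unqualified instruction to resume and nothing in it marks that instruction as subject to exceptions.

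Second, the examples in Table 2's Medical Monitor sentence are not exhaustive. Airway compromise would ordinarily count as serious or severe; the scale in Appendix 6 grades angioedema 3 and anaphylaxis 4. This is fair: the lack of a mention does not put airway compromise outside that step. But the step is a discussion, not a bar.

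Third, Section 4.3.2.1 also cites the pharmacy manual, which was not available, so what sites had in hand is unknown. That stands as a limit on any statement about practice. It does not alter what the protocol says.

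Fourth, Section 1.2.2 reports the drug as generally well tolerated with no adverse drug reactions identified, and no statistical quantity is touched. Both points are accepted. They bear on how often the conflict would matter, not on whether it exists. It is also better described as an internal inconsistency than as a disputed design choice.

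**Conclusion.** The concern holds. On resumption the two texts contradict each other directly: three of the four bars in Section 5.1.3.2 are absent from Table 2, and staff who follow Table 2 as written can breach the protocol's own safety rule. The stop-or-slow difference is real but secondary.

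The conclusion rests on the protocol text alone. It assumes nothing about the pharmacy manual and nothing about how often reactions occur; without a reaction rate, the number of patients or infusions affected cannot be given. It should be corrected because it concerns restarting an infusion after potentially dangerous reactions and the sponsor has already written the safer rule elsewhere in the same document.

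**What to change.** Let the stricter rule govern and print it in both columns of Table 2, along these lines:

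- Mild reaction: slow or halt the infusion.
- Moderate-to-severe reaction: stop at once.
- No restart at that visit after mucosal involvement, airway compromise, symptomatic hypotension with supine systolic pressure below 90, or a second reaction.

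A shorter alternative is one line in Table 2 saying that Section 5.1.3.2 governs wherever the two differ. Align the pharmacy manual if it repeats Table 2, and settle the restart rate in the same edit.

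The cost is one protocol clarification and one site memo. A few more doses may be left incomplete; that number cannot be estimated without a reaction rate. Sample size and data collection do not change.

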The double-blind treatment period of the study includes a baseline visit (of up to 15 days; extensions to the 15-day baseline visit period [e.g., to complete [¹⁸F]GTP1 PET imaging] may be granted on a case-by-case basis by the Medical Monitor), a 68-week treatment period (Weeks 1–69), and an efficacy assessment period (baseline to Week 73). Treatment with study drug will occur Q2W for the first three doses (i.e., doses at Weeks 1, 3, and 5) and Q4W thereafter, up to and including the Week 69 dose (for a total of 19 doses). There will be no administration of study drug at the Week 73 visit. Safety, efficacy, PK, and biomarker assessments will be performed at baseline (during screening, the baseline visit, or at the Week 1 visit, prior to initiation of study drug) and at several postbaseline visits, including the Week 73 visit. See [Appendix 1](#) for details regarding study activities during the double-blind treatment period.

Open-Label Extension Period

[figure not shown]
An optional 96-week OLE period is available to patients who complete the double-blind treatment period and who, in the judgment of the investigator, would potentially benefit from open-label MTAU9937A treatment. For the OLE period, all patients will receive MTAU9937A 4500 mg IV. Safety and efficacy assessments during the OLE period will

be performed at a schedule similar to that of the double-blind treatment period. The procedure(s) performed for tau-based biomarker evaluation during the OLE period ($[^{18}\text{F}]\text{GTP1}$ PET imaging and/or LP) should match the procedure(s) performed during the double-blind treatment period; LP will remain optional, but encouraged, for any patient who continues with longitudinal $[^{18}\text{F}]\text{GTP1}$ PET imaging and had a screening or baseline LP. See [Appendix 2](#) for details regarding study activities during the OLE period.

Safety Follow-Up Period

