5.3.5.1 Infusion-Related Reactions

Adverse events that occur during or within 24 hours after administration of study drug or [¹⁸F]GTP1 or an amyloid radioligand and are judged to be related to study drug infusion or [¹⁸F]GTP1 or an amyloid radioligand should be captured as a specific diagnosis (e.g., "infusion-related reaction," "anaphylactic reaction") on the Adverse Event eCRF. If possible, avoid ambiguous terms such as "systemic reaction." Associated signs and symptoms should be recorded on the dedicated Infusion-Related Reaction eCRF. If a patient experiences both a local and a systemic reaction to the same dose of study drug, [¹⁸F]GTP1, or an amyloid radioligand infusion, each reaction should be recorded separately on the Adverse Event eCRF with signs and symptoms recorded separately on the dedicated Infusion-Related Reaction eCRF.

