Appendix 1 Schedule of Activities (cont.)

- i Only perform assessment if discontinuation visit is ≥ 16 weeks after last assessment for this instrument or procedure. However, if the patient discontinues study drug because of an infusion-related reaction, concurrent ADA and PK samples will also be collected at 12 weeks after the last administration of study drug.
- j Includes respiratory rate, pulse rate, and systolic and diastolic blood pressure while the patient is in a seated position, and temperature. Record abnormalities observed at baseline on the General Medical History and Baseline Conditions eCRF. At subsequent visits, record new or worsened clinically significant abnormalities on the Adverse Event eCRF. On study drug treatment visits, vital signs should be collected 0–4 hours prior to infusion and 60–90 minutes after completion of infusion.
- k Vital signs should be assessed on the same day(s) that the [^{18}F]GTP1 PET scan and/or LP are performed. Vital signs should be assessed just prior to injection of [^{18}F]GTP1 or initiation of the LP procedure, but no earlier than 1 hour prior to injection of [^{18}F]GTP1 or initiation of the LP procedure. Vital signs should also be assessed just after injection of [^{18}F]GTP1 or conclusion of the LP procedure, but no later than 1 hour after injection of [^{18}F]GTP1 or conclusion of the LP procedure.
- l Includes evaluation of the head, eyes, ears, nose, and throat, and the cardiovascular, dermatological, respiratory, and gastrointestinal systems. In addition, the musculoskeletal and genitourinary systems should be examined as clinically indicated. Record abnormalities observed at baseline on the General Medical History and Baseline Conditions eCRF. At subsequent visits, record new or worsened clinically significant abnormalities on the Adverse Event eCRF.
- m Perform a limited, symptom-directed examination at specified timepoints or as clinically indicated. Record new or worsened clinically significant abnormalities on the Adverse Event eCRF.
- n If amyloid PET is used to confirm amyloid positive eligibility, an LP will not be performed as part of screening. If amyloid PET result suggests a patient is amyloid negative, an LP may be performed as part of screening to re-assess amyloid positivity eligibility on the basis of CSF.

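### Table 2, read alone, sets the next infusion's starting rate only from reactions during the prior infusion, so a non-serious Grade 1–2 reaction that begins afterwards leads to a 3.0 mL/min start

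*Protocol*

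**What the plan says.** The Subsequent Infusions column of Protocol Table 2 has two rules for the next starting rate.

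- Slow start: "If the participant experienced an infusion-related or hypersensitivity reaction during the prior infusion, begin infusion at an initial rate of 0.5 mL/min", after which the first-infusion steps are followed.
- Fast start: if the prior infusion was well tolerated, "defined by an absence of Grade 2 reactions during a final infusion rate of 3.0 mL/min), begin infusion at a rate of 3.0 mL/min".

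A third rule in that column acts within a single infusion. If a reaction develops the infusion is stopped or slowed, and once the reaction resolves the site may "resume the infusion at a 50% reduction in rate (i.e., 50% of rate being used at the time that the reaction occurred".

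Elsewhere the Protocol looks past the end of the infusion. Section 5.1.1.1: "All participants will be monitored for infusion reactions, hypersensitivity, or hypersensitivity-like reactions during the infusion and immediately afterwards". Section 5.3.5.1 has sites record as a specific diagnosis, such as an infusion-related reaction, "Adverse events that occur during or within 24 hours after administration of study drug" that are judged related to it. Footnote j of Appendix 1 and footnote f of Appendix 2 schedule vital signs "60–90 minutes after completion of infusion".

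Section 4.3.2.1 also makes the pharmacy manual a governing source for administration: "MTAU9937A will be prepared and diluted into 100-mL IV bags according to the pharmacy manual", with infusions given according to both Table 2 and that manual.

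**The concern.** The Protocol watches for and records reactions that start after the infusion, but the rule that sets the next starting rate does not use them. Table 2 is not silent about such a patient: its definition of a well-tolerated infusion is met, so it directs a start at 3.0 mL/min, six times the stepped starting rate (3.0 / 0.5).

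Take localized urticaria, which Appendix 6 lists as a Grade 2 allergic reaction. If it appears in the last five minutes of an infusion running at 3.0 mL/min, the next infusion starts at 0.5 mL/min. If it appears five minutes after the end, the next infusion starts at 3.0 mL/min. The documents give no reason for treating the two differently. The scheduled post-infusion vital-sign check lies wholly outside the period that the rate rule considers, whatever the infusion's length.

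What is at stake is the caution applied at one later infusion in a patient who has just reacted. No endpoint, estimate or error rate depends on it.

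**Working it through.** **Applying Table 2 literally, prior infusion ending at 3.0 mL/min**

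- Grade 2 reaction while running at 3.0 mL/min: slow-start rule met, fast-start rule not met. Next start 0.5 mL/min.
- Non-serious Grade 1 or 2 reaction beginning after the end: slow-start rule not met, fast-start rule met. Next start 3.0 mL/min.
- Serious or severe reaction: Table 2 and Section 5.1.3.2 require discussion with the Medical Monitor. Not part of this point.

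**Looking for another rule that sets the next rate**

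- Section 4.5 requires a toxicity assessment before each dose. It decides whether to dose.
- Section 5.1.3.1 allows temporary suspension for related toxicity, and Section 4.6.1 requires permanent discontinuation in specified circumstances. Neither sets a rate.
- Section 5.1.3.2 gives half-rate restarts within the same infusion.
- The SAP does not address infusion rates.

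No available text gives a different starting rate for the second case.

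**Infusion times**

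Inputs from Table 2: 30 min at 0.5 mL/min, 30 min at 1.0 mL/min, then 3.0 mL/min. The total volume V is an assumption, because Section 4.3.2.1 gives a 100-mL bag size but no number of bags per dose.

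- Volume given in the two slow steps: 30 × 0.5 + 30 × 1.0 = 45 mL.
- Stepped start: 60 + (V − 45) / 3 min. Direct start: V / 3 min.
- V = 100 mL: 60 + 55/3 = 78.3 min versus 33.3 min.
- V = 200 mL: 60 + 155/3 = 111.7 min versus 66.7 min.
- V = 300 mL: 60 + 255/3 = 145 min versus 100 min.
- Difference: 60 − 45/3 = 45 min for any V of at least 45 mL.

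**How many infusions Table 2 governs**

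Section 3.1.1.1 has dosing at Weeks 1, 3 and 5 and then every 4 weeks, "up to and including the Week 69 dose (for a total of 19 doses": 3 + (69 − 5)/4 = 19, of which 18 are subsequent infusions. Appendix 2 has open-label doses from Week 77 to Week 169: (169 − 77)/4 + 1 = 24. These are the infusions to which the rule applies, not the infusions affected. An affected infusion is one that follows a delayed, non-serious Grade 1–2 reaction after an infusion ending at 3.0 mL/min. The documents give no frequency for such reactions.

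**The case against.** The strongest reply is that part of the governing text is unseen. The pharmacy manual may already deal with delayed reactions, so the result above is what Table 2 says alone, not necessarily what sites are told. That stands.

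It can also be said that Section 5.3.5.1 is a recording rule and Section 5.1.1.1 a monitoring rule. Neither has to match the trigger for an infusion rate, and an investigator might read the slow-start rule in the light of the 24-hour window. This stands in part: the windows need not coincide, and the generous reading is reasonable. But it conflicts with the fast-start rule's own definition, so sites could act differently on the same event.

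Third, the benefit is unproven. The documents do not show that delayed reactions depend on the starting rate, and Section 1.2.2 reports that no adverse drug reactions have been identified. The affected patient has also already received V − 45 mL (stepped) or V mL (direct) at 3.0 mL/min, that is 55 or 100 mL if V is 100 mL. All this is fair. However, a patient who reacts while running at 3.0 mL/min has also been exposed to that rate, and Table 2 still returns that patient to the stepped start. The proposal extends the plan's own logic.

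Finally, pre-dose assessment, suspension, monitoring, the stop-or-slow rule and the anaphylaxis precautions in Appendix 5 limit the consequence. They do, though none sets the starting rate.

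A reader might infer more than the documents support: that severe reactions are ignored (they go to the Medical Monitor), that patients are put on an untested rate (both starts are protocol regimens), or that 18 double-blind and 24 open-label infusions are affected (those are only the infusions the rule governs).

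**Conclusion.** The point holds as a minor patient-safety matter and a cheap improvement. Table 2, taken by itself, classes an infusion ending at 3.0 mL/min and followed only by a non-serious Grade 1–2 reaction as well tolerated, and directs a 3.0 mL/min start. That sits badly with the Protocol's own post-infusion monitoring and 24-hour recording window.

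The conclusion rests on a literal reading of Table 2 and on the pharmacy manual not saying otherwise. How many infusions are affected is unknown, and no risk figure can be given. The 45-minute difference holds for any volume of at least 45 mL; the absolute infusion times depend on the assumed volume. The documents do not support reading this as a demonstrated hazard or as a threat to any trial result.

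**What to change.** Replace the two starting-rate bullets in Table 2 with one rule, for example: *After any infusion-related or hypersensitivity reaction during the prior infusion or within 24 hours after it, or if the prior infusion did not reach 3.0 mL/min, begin at 0.5 mL/min and follow the first-infusion instructions; otherwise begin at 3.0 mL/min.* Check the pharmacy manual and align it if it differs.

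The 24-hour window is already in Section 5.3.5.1, so sites need no new definition. The single rule also settles the residual case of a Grade 1 reaction at 3.0 mL/min with the rate left unchanged, which at present meets both bullets.

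The cost is a wording change, a check of the manual and a letter to sites. Each reaction adds about 45 minutes to one infusion. If that stepped infusion is tolerated and reaches 3.0 mL/min, the next returns to the fast start. No visits or tests are added, and no statistical figure changes.
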